## Revision History

revision #	version date	summary of revisions	consent form changed
	10/13/2013	Original IRB approval	n/a
1	10/20/2014	
prior to enrollment start –formatting change to match the Cancer Center’s template (see details in the last bullet) and the following revisions:
 
 
• Title page delete [name] as a co-investigator as she has left the institution
 
• Minor clarifications to the inclusion/exclusion criteria
 
• Section 8 – Tests and Procedures: move research related tests and procedures from Study Entry to during BMT work-up period
 
• Section 8 - Research specimens will be batched tested in UMN Cytokine Lab (previously using Advanced Research and Diagnostic Laboratory)
 
• Section 8.1.3 – clarified subject reimbursement and compensation
 
• Section 12.5 – early stopping rule for excessive toxicity
 
• Replaced Amplatz with Masonic throughout document when referring to UMN Children’s Hospital
 
• Updated protocol to Cancer Center template: 
 
• Update document cover page to list affiliate institution
 
• Add Sponsor and site PI contact information to page 2
 
• Added revision history page and schema
 
• Section 6 - Added subject registration and randomization in OnCore
 
• Section 9 - Replaced previous AE reporting section with new Event Monitoring, Documentation and Reporting section which includes a new targeted toxicity form (appendix IV), affiliate institution reporting requirements and updated IRB reporting requirements
 
• Section 10 – New section covering study status update, data management, compliance with the Cancer Center’s Data and Safety Monitoring Plan, affiliate monitoring and record retention
 
• Section 13 – New section addressing ethical and regulatory considerations
 
• Move Vitamin D/calcium supplementation and questionnaires to appendix II - IV, add eligibility checklist as appendix I
 
 
 
	yes
2	12/03/2014	
 
• Throughout protocol: Revise Day 100 to Day 90 and if appropriate generalize the time point as 3 months
 
• Throughout protocol: Delete references to study entry as “day of admission for transplant”
 
• Throughout the protocol refer to affiliate institution as Fred Hutchinson Cancer Research Center as this is where the PI and IRB are located, although the study will continue to be conducted at Seattle Children’s Hospital
 
• Section 6.2, Randomization Day 90 Post-HCT Visit: Add statements that we will request to collect data from routine tests (DXA scans done at 1 year post-transplant and other relevant data) from subjects who are not eligible for or refuse randomization at Day 90
 
• Section 7.2, Calcium: Clarify how calcium level will be calculated if
 
	yes

revision #	version date	summary of revisions	consent form changed
		
subject's total calcium level is below the normal range.
 
 
• Section 7.6 and 7.7, Duration of Study Treatment and Participation Update and clarify
 
• Section 8, Study Related Tests and Procedures: Update
 
• Section 8.1.3 Subject Compensation: Update
 
• Section 8.2.5 Diet and Activity Questionnaire: Update to reflect that subjects will receive paper copies of forms
 
• Section 8.3.2 Specimen Processing and Storage: Clarify that research samples will be stored for batch testing and destroyed once testing is complete.
 
• Delete appendix V – Targeted Toxicities as replaced by a more detailed CRF
 
	
3	02/09/2015	
 
• Study synopsis, section 2: remove references to Pfizer as a generic form of pamidronate will be purchased for the study
 
• Section 2.5: Clarify that at the end of study and after drug reconciliation, any remaining pamidronate will be destroyed per local institutional policy
 
• Synopsis, sections 4, 7.3.1, and 8.1: Pamidronate administration – dose will be based on actual body weight or ideal body weight if overweight, to a maximum dose of 60 mg, give over 4 hours, previously over 3 to 4 hours, post infusion flush of 20 cc's will be given at the same rate as the pamidronate, previously over 1 hour
 
• Section 5.2 and checklist – add history of a primary bone malignancy involving the lumbar spine as an exclusion criterion
 
• Sections 7.3.5 and 8.1: Expand birth control options from oral only to include the contraceptive patch or other effective methods
 
• Section 8.1: delete medical history at days 7 and 21, add record of medication usage at screen/study entry and at every study visit beginning with day 21
 
• Section 8.1.3: further clarify participant reimbursement and add "guidelines" to the section header as reimbursement schedule may differ between institutions
 
• Section 8.2.3: update to match changes to 8.1
 
• Section 9.2: delete day 360 as no pamidronate is given
 
• Minor edits and clarifications throughout
 
	yes

revision #	version date	summary of revisions	consent form changed
4	09/29/2015	
 
• Section 5.1.1 – clarify eligible diseases
 
• Section 6 and appendix I – delete reference to eligibility checklist as an eligibility case report form is used instead
 
• Sections 6.2, 7.3.2 and 7.3.5 – clarify randomization time window of <math>\pm 14</math> days and time window in association with lab tests required for randomization (within 10 days prior for vitamin D and 72 hour hours prior for creatinine, pregnancy testing)
 
• Sections 6.2, 7.3.6, 7.5, and 7.7 – add disease relapse/progression as ineligibility for randomization and a reason to go off study and follow-up will end if in person post-transplant follow-up ends
 
• Section 7.3.1 – add a 72 hour window prior for lab work in association with the pamidronate infusion, clarify that laboratory testing procedures (blood, urine) must be collected prior to pamidronate infusion, but consultations, day 90 DXA and day90 pQCT may occur after the infusion as long as done in the <math>\pm 14</math> day window
 
• Sections 7.3.1, 8.1 footnote and 8.3.2 – remove language regarding 1st of the day timeframe for urine collection and add “A morning collection is preferred, but not mandatory. The time of the urine collection must be recorded.”
 
• Section 8 – add a row for randomization on day 90 and refer reader to section 6.2
 
• Section 8.1 and 8.2.3 - add a row for height and weight only and add X under days 180 and 270, delete physical exam and anthropometrics for these days ; update text in section 8.2.3
 
• Section 8.1 - permit Vitamin D level to be drawn at screen or study entry
 
• Section 8.2.4 – clarify DXA scan requirements
 
• Section 9.5 – add a row to the required reporting table for stopping rule events
 
• Appendix III – delete question regarding type of milk consumed and replace with a question regarding formula use
 
	yes
5	02/01/2016	
 
• Synopsis, Sections 4, 5 - expand enrollment to include persons <math>\leq 20</math> years of age
 
• Section 5.2.1 - delete previous HCT from exclusion criteria
 
• Section 12.5 – revise in response to DSMC concerns
 
• Section 8.1 – increase window for DEXA scan to 6 weeks
 
• Section 5.1.4 – remove language surrounding age of assent as this is a multi-center study
 
	Yes
6	4/27/2016	
 
• Section 5.2.9 – clarified eligibility; the intent was to exclude investigational drugs that either can interact with pamidronate or have an independent effect on the primary endpoint (bone mineral content/density), not all investigational drugs.
 
• Section 6.2 – permit Vitamin D level to be drawn 14 days (instead of 10 days) prior to randomization to account for time for lab to send back result.
 
	No

revision #	version date	summary of revisions	consent form changed
7	12/02/2016	
 
Throughout protocol - University of Minnesota Principal Investigator and IND Holder was changed from [name] to [name].
 
Section 7.1 and Appendix II, clarified timing of repeat Vitamin D levels.
 
Section 8.1 and 8.2.2 pregnancy test may be either urine or serum
 
Section 8.2.4 Added that it is not necessary to repeat a lumbar spine x-ray if previously performed within past 12 months
 
Section 10.4 and 10.5 updated link to the Masonic Cancer Center DSMP
 
	Yes
8	05/21/2017	
 
Added non malignant diseases to study eligibility
 
Updated and clarified Vitamin D and Calcium supplementation guidelines (Section 7.3 and Appendix II)
 
Updated laboratory reference ranges to current standards
 
	Yes
9	11/30/2017	
 
Section 5.2 added inability to complete DEXA scan at randomization
 
Section 6.2 clarified testing windows for randomization and randomization procedure
 
Clarified Vitamin D and Calcium supplementation guidelines (Section 7.3)
 
Section 7.5 added sedation option to DEXA scan, and risks of
 
Sections 8.1, 8.2.3, clarified schedule of height and weight evaluations
 
Section 9.2, clarified that AEs will not be reportable if they occur prior to randomization
 
Removed Appendix II as it was a repeat of tables already in the protocol
 
Section 10.3 updated data capture method
 
Appendix III added “completed by” line to the assessment tools
 
	
9A	04/16/2018	
 
Section 9.2 revised and clarified AE reporting procedures
 
	No
10	07/11/2019	
 
Section 7.3 Updated supplementation guidelines for clarity and consistency
 
Section 8.1 added footnote to timing of procedures
 
	No

## Study Summary

### Prevention of Bone Loss After Pediatric Hematopoietic Cell Transplantation

IND Sponsor/ Investigator	[name] Director, Leo Fung Center for Congenital Adrenal Hyperplasia and Disorders of Sex Development University of Minnesota Masonic Children's Hospital
Phase	Phase 2
Study Design	
This is a Phase 2, open-label, randomized, controlled clinical study of pediatric subjects treated with pamidronate with calcium and vitamin D versus calcium and vitamin D alone following hematopoietic cell transplantation (HCT).
 
Subjects randomized to pamidronate treatment will receive infusions at approximately Day 90, Day 180, and Day 270 post-HCT.
 
Laboratory evaluations, dual-energy X-ray absorptiometry (DXA), and peripheral quantitative computed tomography (pQCT) will be performed at specified time points to evaluate safety and treatment efficacy.

Primary Objective	To test the hypothesis that subjects receiving pamidronate with calcium and vitamin D (Pamidronate Group) will have higher lumbar spine bone mineral content (LBMC; adjusted for height, age, sex, Tanner stage, and race) measured by DXA at 1 year post-HCT than subjects receiving calcium and vitamin D alone (Control Group).
Secondary Objectives:	
To test the following hypotheses:
 
 
• Subjects treated with pamidronate will have higher total body BMC (TBMC; excluding head; adjusted for height, age, sex, Tanner stage, and race) measured by DXA 1 year post-HCT compared to the Control Group.
 
• Subjects treated with pamidronate will have higher total bone mineral density (BMD), cortical BMD, trabecular BMD, and estimated bone strength measured by pQCT 1 year post-HCT compared to the Control Group.
 

Correlative Objectives:	
 
• Cytokine levels will increase rapidly in the first 3 weeks after HCT, preceding an increase in markers of bone resorption.
 
• In the Control Group, increased cytokine levels and receptor activator of nuclear factor-<math>\kappa</math> B ligand (RANKL)/osteoprogenin (OPG) ratio 3 weeks post-HCT will be associated with decreased BMC and BMD at 1 year post HCT.
 
• Markers of bone resorption will increase in the first three months after HCT, will remain elevated until at least Day 180 in the Control Group, but will decrease after initiation of pamidronate at Day 90 in the Pamidronate Group.
 
• Markers of bone formation, including osteocalcin (OCN) will decrease in the first three months after HCT and in the Control Group lower OCN levels at Day 90 will be associated with lower BMC and BMD 1 year post-HCT.
 

Duration of Study Participation	1 year from HCT
Number of Subjects	60 evaluable patients (30 per site) over 3.5 years

Main Inclusion Criteria	Subjects will be $\geq 1$ and $\leq 20$ years of age at the time of enrollment and receiving an allogeneic HCT for a hematologic malignancy in complete remission and using a myeloablative preparative regimen, non-malignant diseases with a myeloablative or non-myeloablative preparative regimen, or severe aplastic anemia (SAA) for which any conditioning therapy is permitted.
Standard Therapy	All Subjects - Standard supplementation with calcium and vitamin D beginning at admission to the hospital (prior to HCT) and continuing until post-HCT Day 360 visit
Study Product, Dose, Route, Regimen	Pamidronate Group Only Pamidronate disodium single 1 mg/kg intravenous infusion administered every 3 months for 3 doses - post-HCT Days 90, 180 and 270.
Endpoints	The primary study endpoint is lumbar bone mineral content (LBMC).  Other endpoints are TBMC (excluding head), bone strength, total BMD, cortical BMD, trabecular BMD, levels of markers of bone turnover, cytokines, RANKL/OPG ratio, and body composition.
Statistical Methods	The primary analysis will compare the Pamidronate and Control Groups according to LBMC measured by DXA using a t-test applied to all available Day 360 measurements. A secondary analysis will use multiple imputation to impute Day 360 BMC and BMD measurements for each subject who does not provide one.

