## **12 Statistical Considerations**

### **12.1 Sample Size**

Sixty (60) subjects total (30 each in the Control and Pamidronate groups) gives 80% power to detect a difference between groups of 0.75 standard deviations (SDs)

describing variation in LBMC within study group after adjusting for height, age, sex, Tanner score, and race. Adjusting for age and sex, this SD is 5-8g (46, 47); adjusting further for race and height should reduce this SD by about half (48-50). This gives a within-group SD of about 2.5-4g and a detectable difference of 2-3g. To have 60 evaluable subjects, 192 need to be screened to allow for a 50% consent rate, 10% death rate by Day 90, 20% death rate between Day 90 and Day 360, and 10% drop out after randomization.

Anticipated Enrollment Over Duration of Study

	Screen	Study Entry Day -14 a	Day 7	Day 14	Day 21	Day 90	Day 180	Day 270	Day 360
Total	192	96	96	96	96	86	86	86	60
University of Minnesota (UMN)	96	48	48	48	48	43	43	43	30
Fred Hutchinson Cancer Research Center	96	48	48	48	48	43	43	43	30
a Day 0 is the day of hematopoietic cell transplantation (HCT).									

According to data from 2011 to 2012, 36 allogeneic transplants have been performed at UMN and 37 have been performed at Fred Hutchinson Cancer Research Center. It is expected that screening 28 patients per year will be feasible for both sites.

It anticipated that enrollment will take 3.5 years.

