## 12.2 Subject Population(s) for Analysis

All randomized subjects will be included in the primary analysis according to their randomized treatment assignment, consistent with the principle of intention-to-treat.

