Control Group, but will decrease after initiation of pamidronate at Day 90 (Aim 3 Hypothesis 1), the test of changes up to Day 90 will use the same type of analysis as for Aim 2 Hypothesis 1 but with up to 5 measurements (Day -14 to Day 90). Tests of changes after Day 90 will include all available data for each subject and use a mixed linear model to account for correlation of measurements within subject; changes over time will be tested separately in the Pamidronate and Control groups using contrasts and compared between groups by testing the interaction of group and measurement time (i.e., Day 180, Day 360).

For the hypothesis that markers of bone formation, including osteocalcin (OCN) will decrease in the first three months and in the Control Group lower OCN levels at Day 90 will be associated with lower BMC and BMD 1 year post-HCT (Aim 3 Hypothesis 2), the test of change in OCN to Day 90 will use all available data and the same type of analysis as for Aim 2 Hypothesis 1; the test of change from Day 90 to Day 360 will use control subjects only and simple linear regression with outcome each of the BMC and BMD measures at Day 360 and predictor OCN level at Day 90.

For analyses of Aims 2 and 3 and Aim 1 hypothesis 2, further secondary analyses will use multiple imputation to impute missing measurements. Finally, exploratory analyses will explore risk factors for bone loss, including sex, BMI percentile, LBM adjusted for height, calcium and vitamin D intake, CNS radiation, TBI vs. no TBI in conditioning regimen, donor stem cell source (cord blood vs. other), physical activity, and glucocorticoid exposure for prophylaxis or treatment of GVHD. Subjects who experience a bone fracture after HCT will be excluded from analyses of bone turnover markers but otherwise will be included in all analyses.

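### The secondary multiple imputation makes no exception for death, so on the plan's own attrition figures about two thirds of the imputed Day 360 bone values would belong to children who have died

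*Combined protocol and SAP*

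**What the plan says.** The plan describes imputation in two places.

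- **Study Summary, Statistical Methods:** "A secondary analysis will use multiple imputation to impute Day 360 BMC and BMD measurements for each subject who does not provide one".
- **Section 12.4:** "For analyses of Aims 2 and 3 and Aim 1 hypothesis 2, further secondary analyses will use multiple imputation to impute missing measurements". Section 12.4 uses Aim 1 Hypothesis 2 for the pQCT outcomes. The between-arm comparison of lumbar BMC (LBMC), which is the primary analysis, is not in this list, and neither is total-body BMC (TBMC). BMC enters only through Aims 2 and 3, where Day 360 BMC and BMD are the outcomes of regressions in the Control Group.

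Neither place separates a measurement that a living child missed from one that cannot exist because the child died.

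On the analysis set, section 12.2 states: "All randomized subjects will be included in the primary analysis according to their randomized treatment assignment". The Summary and section 12.4 both base the primary analysis on the Day 360 scans actually obtained. Section 12.1 allows for "10% death rate by Day 90, 20% death rate between Day 90 and Day 360, and 10% drop out after randomization". Section 7.8 promises only attempts to learn survival status after withdrawal or transfer of care. Section 10.2 places reports of deaths in OnCore.

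**The concern.** A child who leaves the study alive has a Day 360 bone mass that nobody measured, and imputation is a reasonable attempt to recover it. A child who died has no Day 360 bone mass. Read literally, the plan treats the two alike and fills both gaps from a model fitted to survivors.

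The result would be an effect in a population where nobody dies, which is not a question the protocol poses. It would also be a weak check on drop-out. If most imputed values concern deceased children, agreement or disagreement with the available-case result says little about whether losing living children mattered. The trial is open-label, so whether deaths are imputed should be settled in writing before the data are analysed.

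**Working it through.** **Inputs (section 12.1 and its enrolment table).** 192 screened; 50% consent; 10% die by Day 90; 20% die between Day 90 and Day 360; 10% drop out after randomisation. The table shows 96 at study entry, 86 at Day 90 and 60 at Day 360.

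**Step 1: reproduce the plan's 60.**
- Enrolled: 192 × 0.50 = 96.
- Reaching Day 90: 96 × 0.90 = 86.4 (table: 86).
- With a Day 360 value, rates added: 86 × (1 − 0.20 − 0.10) = 60.2, which matches 60.
- With the rates compounded instead: 86 × 0.80 × 0.90 = 61.9. The additive reading is the one that gives the stated figure.

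**Step 2: who is missing at Day 360 among those randomised.**
- Deaths: 86 × 0.20 = 17.2.
- Drop-outs: 86 × 0.10 = 8.6.
- Total missing: 25.8 (table: 86 − 60 = 26).
- Death share: 17.2 / 25.8 = 67%, or 17.2 / 26 = 66% against the table.
- Share of a completed set of 86: 17.2 / 86 = 20%.

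**Step 3: other readings of the same rates.**
- Drop-out applied to survivors: 68.8 × 0.10 = 6.9 drop-outs; 17.2 / (17.2 + 6.88) = 71%.
- Death applied to those who did not drop out: 77.4 × 0.20 = 15.5 deaths; 15.48 / (15.48 + 8.6) = 64%.

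**Step 4: if the 10% is wrong.** It has to cover withdrawal, relapse off study, and missed or failed scans. Holding deaths at 20% and taking non-death loss as an assumption (additive):
- 5% non-death loss: 0.20 / 0.25 = 80%.
- 20% non-death loss: 0.20 / 0.40 = 50%.

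**Step 5: pQCT outcomes (University of Minnesota only).** The table goes from 43 to 30, so 13 are missing. Deaths: 43 × 0.20 = 8.6, or 66%. The problem is therefore present under section 12.4 alone, whatever is decided about the Summary sentence.

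**Step 6: where the share does not apply.** The table keeps all 96 children through Day 21, so few gaps in the early cytokine and marker series would be deaths. About 96 × 0.10 = 9.6 children are expected to die by Day 90. They are never randomised, so they enter neither the by-arm marker analyses after Day 90 nor the Control Group regressions. For them, at most a marker value up to Day 90 is affected.

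**Step 7: size of a survivors-only imputed set.** 86 − 17.2 = 68.8, about 69.

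**The case against.** The strongest reply is that this is a secondary analysis and that nothing shows it would change a result. If only the outcome is imputed, from the same covariates as the analysis model, multiple imputation returns the complete-case estimate apart from simulation noise. The plan names no auxiliary variables. That is correct as far as it goes, and no bias has been quantified here. It does not remove the problem. A Day 90 DXA is scheduled and is an obvious auxiliary. Section 12.4 does not say which visit supplies the height and Tanner adjusters; if it is Day 360, they too would be missing for deceased children and would need imputing. The meaning of the imputed estimate is also unclear whatever its value.

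A second reply is that section 12.4 governs and the Summary is out of step, since the Summary names a t-test where 12.4 specifies an adjusted regression. On that view the between-arm LBMC comparison has no planned imputation. This has force: deleting the Summary sentence would reconcile the two places as well as extending 12.4 would. The treatment of deaths would still need stating for the pQCT outcomes and the Control Group regressions.

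A third reply is that a sensible statistician would leave deaths out. Probably so, but the Summary's wording covers every subject without a value.

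Some stronger readings are tempting and fail:
- **Deaths would be concealed.** They are recorded in OnCore (10.2), the affiliate reports serious events regardless of attribution (9.4), and the DSMC reviews the study at least quarterly (10.4).
- **Section 12.4 never imputes BMC.** It does, in the Control Group regressions.
- **Imputation is the plan's check on loss for the primary endpoint.** Under 12.4 that is not established.

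**Conclusion.** The point stands as a gap in a secondary analysis. As written, the imputation rule produces Day 360 values for children who have died, and on the planning figures these are about 17 of 26 missing values among randomised children. The share is 64% to 71% across compounded readings of the stated rates, and 50% to 80% if non-death loss is assumed to be 20% down to 5%. It is a planning expectation; the actual share depends on the deaths and losses observed.

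A reader might infer that the primary result is compromised. The documents do not support that: the primary analysis uses observed Day 360 scans, so imputation cannot alter it. What the primary analysis lacks is a plain statement of whom it describes. Section 12.2 refers to everyone randomised, which can be read as fixing analysis by assigned arm, but the available-case estimate covers about 60 of 86. It applies to children alive with a Day 360 DXA, which conditions on events after randomisation.

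A reader might also extend the two thirds to every imputed value, or to children who die before Day 90. Neither follows, for the reasons in step 6 of the working.

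**What to change.** 1. **Summary and section 12.4:** state that no measurement dated after a subject's death is imputed. Impute for subjects not known to have died by that time point, and add a sensitivity analysis limited to those confirmed alive. A strict rule requiring confirmed survival in the main imputation would exclude drop-outs of unknown status, the very group imputation should recover, because section 7.8 promises only attempts to obtain that information.
2. **Reconcile the Summary with section 12.4** on whether the between-arm LBMC and TBMC comparisons are imputed. Either extend the list in 12.4 or withdraw the Summary sentence.
3. **Sections 12.2 and 12.4:** state that the available-case primary estimate applies to children alive with a Day 360 DXA and is conditional on a post-randomisation event. Report deaths and drop-outs by arm beside it.

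The cost is wording only, with no new visits or data. The imputed set falls from 86 to about 69, fewer in the confirmed-alive sensitivity analysis if some drop-outs cannot be traced. The survivor estimate remains conditional on survival, so it needs to be read beside the deaths by arm.
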